For this pilot study, sample size limitations will require the use of surrogate markers of maternal morbidity to serve as patient outcomes, which have been selected based on evidence-based best-practices.¹⁻¹⁴ The primary clinical outcome for this study will be blood pressure measurement obtained three to ten days postpartum. Prespecified secondary outcomes include *postpartum readmission for blood pressure management* (e.g. rehospitalizations within 30 days of discharge), *adherence to evidence-based best-practices* (e.g. medications, antepartum surveillance, blood pressure ascertainment, postpartum blood pressure goal of <140/90), *composite severe maternal morbidity* (i.e. stroke, seizure/eclampsia, posterior reversible encephalopathy syndrome, pulmonary edema, heart failure, myocardial infarction, acute fatty liver of pregnancy, hemolysis, elevated liver enzymes and low platelets, placental abruption, post-partum hemorrhage, blood transfusion, acute kidney injury, and transaminitis), *postpartum maternal mortality*, and *composite neonatal morbidity* (i.e. umbilical artery pH <7.10, umbilical artery lactate, seizures, therapeutic hypothermia, hypoxic-ischemic encephalopathy, mechanical ventilation, intrauterine fetal death, neonatal death). We will also explore patient preferences as to treatment group via the Agency for Healthcare Research and Quality Consumer Assessment of Healthcare Providers and Systems (AHRQ CAHPS) survey and compared between both intervention groups and standard prenatal care.²⁵ CAHPS survey will provide mixed quantitative and qualitative assessments. Our *central hypothesis* is that app-based Bluetooth enabled blood pressure monitoring will improve adherence to evidence-based best practices and will demonstrate signals towards improved health equity and maternal morbidity outcomes compared to SMS-based remote blood pressure monitoring.

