2. STUDY DESIGN, METHODS, AND PROCEDURES

Study Design

2.1 Study Design: We will conduct a *pilot randomized control trial* of **120** women who deliver at Women and Infant's Hospital of Rhode Island (WIHRI) and plan to receive postpartum care at a WIHRI-affiliated clinic. We will use broad inclusion criteria and analyze data using the intention-to-treat principle to increase generalizability of the findings.

2.2 Eligibility criteria: Inclusion criteria: a) English- or Spanish-speaking b) maternal age ≥ 18 years old, c) smartphone ownership for remote blood pressure ascertainment, d) diagnosis of gestational hypertension, preeclampsia, or chronic hypertension, e) plan to receive postpartum care at a Women & Infants Hospital (WIH)-affiliated clinic. Exclusion criteria: a) fetal anomaly, b) prisoners, c) lack of smartphone, and d) inability to consent.

2.3 Screening, consent, and recruitment: Eligible women will be recruited at the Women and Infant's Hospital of Rhode Island (WIHRI) 's obstetrics units (obstetric triage, labor & delivery, antepartum care unit, and postpartum care unit) during their delivery hospitalization. Recruitment will be conducted by a research assistant or study principal investigator or co-investigator.

2.4 Randomization and blinding: Regardless of when their diagnosis of chronic hypertension, gestational hypertension, or preeclampsia with or without features occurs before or during delivery hospitalization, upon hospital discharge all patients will receive an automatic blood pressure cuff from WIHRI if their insurance does not cover this (or if they do not have one already); for patients whose insurance does cover automatic blood pressure cuffs, the provider will provide them with a prescription for this device at time of diagnosis. This is part of WIHRI's equity initiative related to hypertension: as stated previously, WIHRI has committed to provide non-Bluetooth enabled blood pressure cuffs to all eligible patients.

Those who consent to participate in the study, complete baseline study surveys, and receive a blood pressure cuff prior to discharge will be randomized 1:1 via a computer-generated randomization sequence to one of two protocols: *app based remote blood pressure monitoring* (intervention group) or and standard PNC with SMS-based monitoring (comparison group). The study staff will remain blinded to intervention, except for the research assistant who will be, by necessity, unblinded.

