They will receive the following per their randomization group:

Standard care (comparison group)

All women will receive education and counseling from their physician providers on evidence-based best-practices and red-flags for pregnancy's complicated by chronic hypertension, preeclampsia, or gestational hypertension. They will participate in WIHRI's ongoing equity initiative using automatic blood pressure cuffs in a remote hypertension monitoring program supported by a nurse practitioner and community health worker.

App-based remote blood pressure monitoring (intervention group)

Women in this group will receive a Bluetooth-enabled automatic blood pressure cuff that sends messages through an affiliated smartphone application to providers upon recording each measurement. This affiliated smartphone application will also contain education on hypertension management. Upon receipt of the blood pressure cuff, participants will be instructed to set up the program/app such that the research assistant (RA) will receive all recorded blood pressure managements. All patients will receive instructions on how to obtain blood pressure and will be instructed to call their on-call provider if the blood pressure is $>160/110$ mmHg. The RA will review each patient's blood pressure log daily to ensure blood pressures remain mild-range (i.e. 140-159/90-109 mmHg) or less.

2.5 Study procedures: Perinatal data will be collected and directly entered by the research assistant or principal investigators into REDCap, a secure database hosted by WIHRI. Data will be collected on a rolling basis to ensure timely collection and monitoring for unseen adverse events.

Potential challenges and alternative approaches: Obtaining our target sample size may be challenging due to the incidence of hypertension diseases of pregnancy in the literature. However, we anticipate having a sufficient population from which to recruit for this pilot study given the 18 month study period and the relatively small sample study. However, should our target sample size be lower than expected, we may expand recruitment into private practice groups who have separate admitting privileges.

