Since starting recruitment, an additional challenge has developed: up to 10% of participants in the equity program (who may or may not be in the study) are discharged without blood pressure cuffs with the plan for a home visit to provide a BP cuff within 3-7 days after discharge. In addition, about 10% of patients who participated in the study did not complete their baseline study survey. To ensure we obtain a study population of 120 who follow the study protocol, we have developed an alternative approach by changing our inclusion criteria. Specifically, eligible people may be consented and randomized but only those who receive a BP cuff and complete their intake survey prior to discharge will be included in the trial's analytic population. We anticipate needed to randomize up to 160 patients in order to obtain our desired study population of 120 participants.

2.6 Study outcomes and Power:

Primary outcome: The primary outcomes will be adherence to recommended blood pressure check 3-10 days postpartum, as is recommended per standard of care. Our sample size of **120** pregnant women with gestational hypertension or preeclampsia will allow us to detect a 60% increase in adherence to recommended blood pressure check from the baseline rate of 50%, using a two-tailed alpha of 0.05. The 60% improvement (i.e. from 50% to 80% adherence) is conservative as it is less than has been reported in the medical literature.¹⁵⁻¹⁷ **Secondary outcomes:** Secondary outcomes will be surrogate markers of maternal morbidity.

Prespecified secondary outcomes include postpartum readmission for blood pressure management (e.g. hospital admission for blood pressure management within 30 days of discharge), adherence to evidence-based best-practices (e.g. medications, blood pressure ascertainment, postpartum blood pressure goal of $<140/90$), composite severe maternal morbidity (**Table 2**), and composite neonatal morbidity (Table 1). Our study will likely not be powered to detect differences in secondary outcomes due to the rarity of the individual patient outcomes but will provide us crucial pilot data for the subsequent study.

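### Each secondary morbidity composite has two competing component lists and no counting window, so it cannot be scored one way and, for women randomised after birth, includes events that precede allocation.

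*Combined protocol and SAP*

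**What the plan says.** Section 1 sets out both composites as closed lists. The neonatal one is "umbilical artery pH <7.10, umbilical artery lactate, seizures, therapeutic hypothermia, hypoxic-ischemic encephalopathy, mechanical ventilation, intrauterine fetal death, neonatal death". Section 2.6 (outcomes and power) names both composites as prespecified secondary outcomes and sends the reader to Table 2 for the maternal list, but for the other it writes "and composite neonatal morbidity (Table 1". In the text available for this review, both lists stand in Table 2 and no Table 1 appears. Table 1 may have been lost when the PDF was read.

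Other outcomes have windows. The primary outcome is tied to days 3 to 10 postpartum, and readmission is "hospital admission for blood pressure management within 30 days of discharge". Neither composite has a window.

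On timing, Section 2.3 recruits in triage, labour and delivery, "antepartum care unit, and postpartum care unit) during their delivery hospitalization". Section 2.4 says that women who consent, complete the baseline surveys and "receive a blood pressure cuff prior to discharge will be randomized 1:1". Section 2.5 later says that "eligible people may be consented and randomized but only those who receive a BP cuff and complete their intake survey prior to discharge" will enter the analytic population, so randomisation may come first. Section 2.8 places recruitment in prenatal clinics. In the app arm, "Upon receipt of the blood pressure cuff, participants will be instructed to set up the program/app".

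**The concern.** A composite needs a list of components, a rule that turns each into yes or no, and a period over which events count. All three are incomplete here. Two abstractors following the plan could score the same woman or baby differently, and the choice between lists could be made after data are seen.

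Without a start date, events from before randomisation can enter the comparison. Without an end date, women can be followed for different lengths of time.

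The stake lies beyond the pilot. Section 1 intends these data to support an efficacy trial powered on maternal morbidity. An event rate or risk ratio of uncertain content and period is a weak basis for planning that trial.

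**Working it through.** **1. The two lists side by side.** The plan gives no numerical figure for either composite, so there is none to reproduce.

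| Composite | Section 1 | Table 2 | Difference |
|---|---|---|---|
| Maternal | 13 | 11 | Myocardial infarction and blood transfusion only in Section 1 |
| Neonatal | 8 | 9 | Supplemental oxygen only in Table 2 |

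The 11 shared maternal components are abruption, acute fatty liver, acute kidney injury, seizure or eclampsia, heart failure, HELLP, post-partum hemorrhage, posterior reversible encephalopathy, pulmonary edema, stroke and transaminitis. All 8 neonatal components of Section 1 recur in Table 2.

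Three items cannot be scored as they stand:
- Lactate has no threshold in either place, although cord pH does.
- Oxygen is split into four bands from 0-6 hours to beyond 24 hours of life, with none named as the event.
- Section 1 counts transfusion in the composite, yet when it quotes the hospital's severe maternal morbidity rate it leaves transfusion out as unrelated to hypertension.

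**2. Events before allocation.** For a woman randomised after birth, cord pH, cord lactate, intrauterine fetal death and abruption are already settled. Other components may or may not be; the documents do not say when they occur.

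**3. Effect on the maternal risk ratio.** Let *s* be the share of SMS-arm events before randomisation. Assume that early events are equally frequent in both arms and that no woman has both an early and a later event. Then:

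observed RR = *s* + (1 − *s*) × true RR

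The documents give neither *s* nor the true RR, so both are assumed.

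| *s* | True RR 0.50 | True RR 0.70 |
|---|---|---|
| 10% | 0.10 + 0.90 × 0.50 = 0.55 | 0.73 |
| 25% | 0.63 | 0.78 |
| 50% | 0.75 | 0.85 |
| 75% | 0.88 | 0.93 |

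These values do not depend on the base rate.

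**4. Effect on the risk difference, also planned in Section 2.7.** With SMS-arm risk *p*, the difference is *p*(1 − *s*)(1 − true RR), the same with or without a window. Its standard error is √[p₁(1 − p₁)/60 + p₂(1 − p₂)/60], with 60 per arm from Section 2.6. Without a window, p₁ = *p* and p₂ = *p* × observed RR. With one, p₁ = *p*(1 − *s*) and p₂ is half of that. The table takes *p* = 6.6%, the hospital rate in Section 1, as a rough guide only, and true RR 0.50.

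| *s* | Difference (points) | SE, no window | SE, window | SMS-arm events in window |
|---|---|---|---|---|
| 10% | 3.0 | 4.0 | 3.8 | 3.6 |
| 25% | 2.5 | 4.1 | 3.4 | 3.0 |
| 50% | 1.7 | 4.3 | 2.8 | 2.0 |
| 75% | 0.8 | 4.4 | 2.0 | 1.0 |

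Without a window, about 60 × 0.066 = 4 SMS-arm events are expected. The window lowers the standard error, but at 6.6% it still exceeds the difference in every row. That is not so at every base rate: at an assumed 20% with *s* = 10%, the difference is 9.0 points against standard errors of 6.6 (no window) and 6.2 (window).

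The difference stays the same only if the two kinds of event do not overlap. With independent early and later risks of 10% each and true RR 0.50, the SMS arm has 1 − 0.90 × 0.90 = 19.0% and the app arm 1 − 0.90 × 0.95 = 14.5%. That is 4.5 points instead of 5.0.

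**5. Precision in the pilot.** Using log-normal 95% intervals with 60 per arm, 4 against 3 events gives RR 0.75 (0.18 to 3.2). With a window and half the events early, 2 against 1 gives 0.50 (0.05 to 5.4).

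**The case against.** The strongest reply is that these are secondary outcomes in a pilot. Section 2.6 already says the study will probably lack power for them, and the primary outcome does not depend on them. Randomisation balances early events in expectation, so they do not favour either arm. This all stands and limits the severity. It does not excuse an outcome that cannot be scored one way.

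A second reply is that Section 2.6 points to Table 2 for the maternal list, so Section 1 could be read as background. That helps, but Section 1 presents its lists as definitions. Table 2 also leaves lactate and oxygen unscorable.

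A third reply is that the dilution is of unknown size. The early shares are assumed. Section 1 attributes hypertension-related severe morbidity mainly to postpartum hypertension, which favours the low end, where 0.50 becomes only 0.55. That is fair, although the hospital metric and the trial composite are different lists.

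Two stronger readings are tempting. A reader might infer that the arms are scored on different definitions. Nothing supports that: whichever list is used would apply to both arms. A reader might also infer that all or most women are randomised after birth. The documents do not say so. Section 2.3 includes units where women have not yet delivered, Section 2.5 lets randomisation precede cuff receipt, and Section 2.8 names prenatal clinics.

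**Conclusion.** The concern holds in a limited form. The conflicting lists, the unscorable lactate and oxygen items and the absent windows are visible in the text and need no inference. That some counted events precede allocation follows for any woman randomised after birth; the share of such women is unknown.

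The consequence is dilution of the risk ratio and added noise, not systematic bias. An observed ratio of 0.55 to 0.88 for a true 0.50 rests on assumed early shares of 10% to 75%, equal early risk in both arms and no overlap. The risk difference is unchanged in expectation only under that same no-overlap assumption. A window reduces noise, but the pilot's estimates remain imprecise.

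Severity is minor to moderate. The main gain is a composite that can be scored one way and interpreted when it is carried into the later trial.

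**What to change.** Make one documented amendment before outcomes are compared by arm.

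1. Use a single component list per composite in Section 1 and Table 2, and correct the table reference in Section 2.6. Decide on myocardial infarction and transfusion. Give lactate a cut-off or remove it. Decide whether supplemental oxygen stays and, if so, which band counts.
2. Count a maternal component only if its onset is after randomisation, up to one fixed end for all women; the existing 30 days after discharge would serve. Record conditions already present at randomisation as baseline, not as events. Show each component by arm, because delivery events still count for women randomised before birth.
3. Report events before randomisation by arm as baseline descriptors, including neonatal components fixed at birth for women randomised after it. Report later neonatal events descriptively.
4. Reconcile Sections 2.3, 2.4, 2.5 and 2.8 on recruitment site and on whether randomisation precedes cuff receipt.

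The cost is a change to prespecified outcomes after enrolment began ("Since starting recruitment, an additional challenge has developed"). Onset dates must be added to REDCap and retrieved from charts for women already enrolled. Fewer composite events will count. The sample size and the primary analysis do not change.

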2. STUDY DESIGN, METHODS, AND PROCEDURES

Study Design

2.1 Study Design: We will conduct a *pilot randomized control trial* of **120** women who deliver at Women and Infant's Hospital of Rhode Island (WIHRI) and plan to receive postpartum care at a WIHRI-affiliated clinic. We will use broad inclusion criteria and analyze data using the intention-to-treat principle to increase generalizability of the findings.

2.2 Eligibility criteria: Inclusion criteria: a) English- or Spanish-speaking b) maternal age ≥ 18 years old, c) smartphone ownership for remote blood pressure ascertainment, d) diagnosis of gestational hypertension, preeclampsia, or chronic hypertension, e) plan to receive postpartum care at a Women & Infants Hospital (WIH)-affiliated clinic. Exclusion criteria: a) fetal anomaly, b) prisoners, c) lack of smartphone, and d) inability to consent.

2.3 Screening, consent, and recruitment: Eligible women will be recruited at the Women and Infant's Hospital of Rhode Island (WIHRI) 's obstetrics units (obstetric triage, labor & delivery, antepartum care unit, and postpartum care unit) during their delivery hospitalization. Recruitment will be conducted by a research assistant or study principal investigator or co-investigator.

2.4 Randomization and blinding: Regardless of when their diagnosis of chronic hypertension, gestational hypertension, or preeclampsia with or without features occurs before or during delivery hospitalization, upon hospital discharge all patients will receive an automatic blood pressure cuff from WIHRI if their insurance does not cover this (or if they do not have one already); for patients whose insurance does cover automatic blood pressure cuffs, the provider will provide them with a prescription for this device at time of diagnosis. This is part of WIHRI's equity initiative related to hypertension: as stated previously, WIHRI has committed to provide non-Bluetooth enabled blood pressure cuffs to all eligible patients.

Those who consent to participate in the study, complete baseline study surveys, and receive a blood pressure cuff prior to discharge will be randomized 1:1 via a computer-generated randomization sequence to one of two protocols: *app based remote blood pressure monitoring* (intervention group) or and standard PNC with SMS-based monitoring (comparison group). The study staff will remain blinded to intervention, except for the research assistant who will be, by necessity, unblinded.

They will receive the following per their randomization group:

Standard care (comparison group)

All women will receive education and counseling from their physician providers on evidence-based best-practices and red-flags for pregnancy's complicated by chronic hypertension, preeclampsia, or gestational hypertension. They will participate in WIHRI's ongoing equity initiative using automatic blood pressure cuffs in a remote hypertension monitoring program supported by a nurse practitioner and community health worker.

App-based remote blood pressure monitoring (intervention group)

Women in this group will receive a Bluetooth-enabled automatic blood pressure cuff that sends messages through an affiliated smartphone application to providers upon recording each measurement. This affiliated smartphone application will also contain education on hypertension management. Upon receipt of the blood pressure cuff, participants will be instructed to set up the program/app such that the research assistant (RA) will receive all recorded blood pressure managements. All patients will receive instructions on how to obtain blood pressure and will be instructed to call their on-call provider if the blood pressure is $>160/110$ mmHg. The RA will review each patient's blood pressure log daily to ensure blood pressures remain mild-range (i.e. 140-159/90-109 mmHg) or less.

2.5 Study procedures: Perinatal data will be collected and directly entered by the research assistant or principal investigators into REDCap, a secure database hosted by WIHRI. Data will be collected on a rolling basis to ensure timely collection and monitoring for unseen adverse events.

Potential challenges and alternative approaches: Obtaining our target sample size may be challenging due to the incidence of hypertension diseases of pregnancy in the literature. However, we anticipate having a sufficient population from which to recruit for this pilot study given the 18 month study period and the relatively small sample study. However, should our target sample size be lower than expected, we may expand recruitment into private practice groups who have separate admitting privileges.

Since starting recruitment, an additional challenge has developed: up to 10% of participants in the equity program (who may or may not be in the study) are discharged without blood pressure cuffs with the plan for a home visit to provide a BP cuff within 3-7 days after discharge. In addition, about 10% of patients who participated in the study did not complete their baseline study survey. To ensure we obtain a study population of 120 who follow the study protocol, we have developed an alternative approach by changing our inclusion criteria. Specifically, eligible people may be consented and randomized but only those who receive a BP cuff and complete their intake survey prior to discharge will be included in the trial's analytic population. We anticipate needed to randomize up to 160 patients in order to obtain our desired study population of 120 participants.

2.6 Study outcomes and Power:

Primary outcome: The primary outcomes will be adherence to recommended blood pressure check 3-10 days postpartum, as is recommended per standard of care. Our sample size of **120** pregnant women with gestational hypertension or preeclampsia will allow us to detect a 60% increase in adherence to recommended blood pressure check from the baseline rate of 50%, using a two-tailed alpha of 0.05. The 60% improvement (i.e. from 50% to 80% adherence) is conservative as it is less than has been reported in the medical literature.¹⁵⁻¹⁷ **Secondary outcomes:** Secondary outcomes will be surrogate markers of maternal morbidity.

Prespecified secondary outcomes include postpartum readmission for blood pressure management (e.g. hospital admission for blood pressure management within 30 days of discharge), adherence to evidence-based best-practices (e.g. medications, blood pressure ascertainment, postpartum blood pressure goal of $<140/90$), composite severe maternal morbidity (**Table 2**), and composite neonatal morbidity (Table 1). Our study will likely not be powered to detect differences in secondary outcomes due to the rarity of the individual patient outcomes but will provide us crucial pilot data for the subsequent study.

We will also explore patient preferences as to treatment group via the Agency for Healthcare Research and Quality Consumer Assessment of Healthcare Providers and Systems (AHRQ CAHPS) survey and compared between both intervention groups and standard prenatal care.²⁵ Per AHRQ guidelines, 100 CAHPS surveys must be completed in a pilot study to determine a difference in patient experience between care models.²⁵ Our study population of **60 women** per group (120 women total) is anticipated to generate ~100 completed surveys per group (200 total), based on an anticipated response rate of 80% and each participant completing two surveys. Upon enrollment, participants will choose whether they desire to complete the AHRQ CAHPS surveys in paper, online through email, or via a text-message platform; regardless of route, surveys will be collected at randomization and at ~30-45 days postpartum.

On the second survey, participants will also complete a validated scale, the Decision Regret Scale.²⁶ Of note, both the AHRQ CAHPS study and the Decision Regret Study are already validated in Spanish.

2.6 Data Management, Sources of Materials, Records/Data to be reviewed: Antepartum, maternal/neonatal, pregnancy, and perinatal data will be collected and directly entered by the research assistant or principal investigator into REDCap, a secure database hosted by WIHRI. All primary and secondary outcomes will be entered into REDCap by the RA or study team. Thus, the data to be reviewed will only be collected by key study personnel. In addition, pregnancy characteristics (maternal weight, disease comorbidities, etc.) and demographic information (reported race/ethnicity, insurance type, zip code) will be collected post-delivery and entered into REDCap. Prior to data analysis, all patient identifiable information will be stripped to ensure patient confidentiality. Our REDCap database will be encrypted by multiple levels of password protection (accessing computer, network, and logging into database) that will only be accessible by key research personnel. Anti-virus software is installed and up to date and the operating system is up to date with all Windows and Apple updates.

Material/Specimen Management: No specimens will be stored outside of standard care (such as umbilical cord gases processed by laboratory per usual clinical protocol).

Provisions to monitor the data to ensure the safety of subjects: Our study does not involve greater than minimal risk. However, we will monitor for unanticipated adverse outcomes. As a part of this, key study personnel (Drs. [name], [name]) will monitor for adverse outcomes on a weekly basis. Should any unanticipated outcomes be found, this will be reported back to the IRB. Beyond the weekly monitoring of patients/data, this will also be performed globally on a quarterly basis.

Withdrawal of subjects: Patients will not be withdrawn from the study.

2.7 Data analysis: Analysis will follow the intention-to-treat principle. Continuous variables will be compared using the Student's *t*-test or Mann Whitney *U* test, as appropriate. Categorical variables will be compared using the χ^2 or Fisher's exact test, as appropriate. We will calculate crude and unadjusted risk ratios and differences. We will use multivariable logistic regression to adjust for potential confounders. Qualitative data obtained from CAHPS survey will also be analyzed using Nvivo, a computer-assisted qualitative data analysis software provided by Brown University. This software promotes inquiry beyond coding, sorting and retrieval of data. It is designed to integrate coding with qualitative linking, shaping, and modeling that may inform health equitable care. [name] and [name] have used Nvivo software. In addition, [name] has utilized this procedure to capture qualitative data previously to successfully design, implement, and launch a new model of health care for vulnerable patients transitioning from the hospital to sub-acute care facilities.²⁷

